#### 2.4.5.2 Deaths

The following summaries of deaths will be generated.

- Number (%) of patients from the safety population who died by study period (on-study, on-treatment, post-study) and reasons for death as reported by the investigators;
- TEAEs leading to death (death as an outcome on the AE as reported by the Investigator) by primary SOC, HLGT, HLT, and PT sorted by internationally agreed SOC order, with HLGT, HLT, and PT presented in alphabetical order within each SOC, for the safety population. TEAE leading to death are TEAE that led to death regardless of timing of death in relation to IMP injection (i.e. death occurring in the TEAE period or during the post-treatment period).
- Deaths in non-enrolled patients or enrolled but not treated patients;

# 2.4.5.3 Analyses of laboratory variables

The summary statistics (including number, mean, median, Q1, Q3, SD, minimum and maximum) of all laboratory variables (central laboratory values and changes from baseline) will be calculated for each visit or study assessment (baseline, each post-baseline value of the treatment period, last on-treatment and worst on-treatment value). In addition, for some parameters of interest, mean changes from baseline with the corresponding SE could be plotted over time (at same time points). This section will be organized by biological function as specified in Section 2.1.4.3. For glucose, only fasting samples will be summarized.

The incidence of PCSAs (list provided in Appendix A), as well as ALT increase as defined as AESI and hemoglobin decrease from baseline ≥15g/L, at any time during the TEAE period will be summarized by biological function irrespective of the baseline level and/or according to the following baseline status categories:

- Normal/missing
- Abnormal according to PCSA criterion or criteria

Glucose (quantitative summary and PCSA) will also be analyzed, overall and according to the diabetic status at baseline.

For parameters for which no PCSA criteria are defined, similar table(s) using the normal range could be provided.

Property of the Sanofi Group - strictly confidential

If any clinically significant signal is detected and need further characterization, exploration of time to onset will be performed for selected PCSAs assessed during the TEAE period as described below to account for the differential exposure time in all patients.

The incidence rates of selected PCSA during TEAE period at 24, 52, 78, 104 and 156 weeks of exposure will be calculated with Kaplan-Meier methodology, using the midpoint of the time interval between the first assessment with PCSA and the previous assessment. Kaplan-Meier curves will be also provided. Only the first event (PCSA) will be counted. Patients without any event will be censored at the last assessment performed during the TEAE period.

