10.1.1.15 Visit 15/ Week 144/ Month 36 (Day 1009 ± 7)

- Collect adverse events
- Record concomitant medication
- Take vital signs including heart rate and blood pressure
- Get body weight measurement
- Physical examination
- Review patient's diet. Patient should be on a NCEP-ATPIII TLC diet or equivalent.
- Data collection on IMP administration and IMP compliance check by review of diary and treatment kit
- Obtain fasting blood sample for:
 - Lipids: measure and/or calculation of total-C, LDL-C, HDL-C, TG, non-HDL-C, Apo B, Apo A-1, ratio Apo B/Apo A-1, and Lp (a)
 - Hematology
 - Chemistry
 - CPK
 - Liver panel
 - Anti-alirocumab antibodies
- Local urine pregnancy test (females of childbearing potential only).
- IVRS/IWRS contact for allocation of a batch number for treatment kit
- IMP kit dispensation and treatment administration package should be provided. The patient injection instruction manual and diary may be given, as needed.
- Reminders

- An appointment will be given for the next visit.
- Patient to bring the diary and used kits and unused auto-injectors at the next visit.

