#### 2.1.4.3 Laboratory safety variables

Clinical laboratory data consist of blood analysis, including hematology and clinical chemistry. Clinical laboratory values will be analyzed primarily into international units and will also be analyzed into conventional (US) units when applicable.

Unless otherwise specified below, blood samples for clinical laboratories were to be collected at Visit 1 (Week 0), Visit 3 (Week 8), Visit 5 (Week 24), Visit 7 (Week 48), Visit 9 (Week 72), Visit 11 (Week 96), Visit 13 (Week 120), Visit 15 (Week 144) and Visit 17 (Week 168)/or early termination. The laboratory parameters (excluding those considered as efficacy parameters) will be classified as follows:

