# • Clinical chemistry:

- Metabolism: glucose, total protein, albumin, creatine phosphokinase.
- Electrolytes: sodium, potassium, chloride, calcium, phosphorus, bicarbonate.
- Renal function: creatinine, eGFR, blood urea nitrogen, uric acid.
- Liver function (also measured at Week 4, and Week 12, except GGT and LDH): alanine aminotransferase (ALT), aspartate aminotransferase (AST), alkaline phosphatase (ALP), gamma glutamyl transferase (GGT), total bilirubin, and in case of total bilirubin values above the normal range, must include direct and indirect bilirubin, lactate dehydrogenase (LDH).

Technical formulas are described in Section 2.5.1.

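### Midpoint-dated PCSA incidence is read at weeks that do not match the 24-weekly assessments: about 5–8% low at 52, 78 and 104 weeks, and on a step at 156 weeks

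*SAP*

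**What the plan says.** SAP 2.4.5.3 (laboratory variables) plans a time-to-onset exploration of selected PCSAs when a signal needs characterising. Three rules matter.

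- Reading times: "The incidence rates of selected PCSA during TEAE period at 24, 52, 78, 104 and 156 weeks of exposure will be calculated" by Kaplan-Meier.
- Event date: "using the midpoint of the time interval between the first assessment with PCSA and the previous assessment".
- Censoring: "Patients without any event will be censored at the last assessment performed during the TEAE period".

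SAP 2.4.5.4 repeats these rules for vital signs.

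SAP 2.1.4.3 sets the laboratory schedule: "Visit 1 (Week 0), Visit 3 (Week 8), Visit 5 (Week 24), Visit 7 (Week 48), Visit 9 (Week 72"), then "Visit 11 (Week 96), Visit 13 (Week 120), Visit 15 (Week 144) and Visit 17 (Week 168)/or early termination". The extra liver tests come early: "Liver function (also measured at Week 4, and Week 12, except GGT and LDH"). In the Protocol flow chart (1.2), heart rate and blood pressure follow the same 24-weekly pattern from Week 24. Neither document says how readings that fall between assessments are to be understood.

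**The concern.** A midpoint-dated curve is flat between midpoints. When it is read at a week that is neither an assessment nor tied to one, the value belongs to the last assessment whose midpoint has passed, not to the week in the column heading. Here the gap between heading and content is 4, 6 and 8 weeks at 52, 78 and 104 weeks, and it is undefined at 156 weeks because that reading falls on a step.

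These tables would be made when a signal is being followed over long exposure, in an uncontrolled study whose primary objective is long-term safety. If the early columns are low and the last is not, a steady risk can look like a late increase. No concurrent control arm would show the same pattern and expose it. Because the shift comes from the reading rule, a larger sample would not remove it.

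**Working it through.** The plan gives no figure to reproduce, so the check uses its rules and schedule.

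**Inputs from the documents.** Assessments at Weeks 0, 8, 24, 48, 72, 96, 120, 144 and 168 (SAP 2.1.4.3). Liver panel, heart rate and blood pressure also at Weeks 4 and 12. Visit windows of ±7 days (Protocol 1.2). Week 144 is "Visit 15/ Week 144/ Month 36 (Day 1009 ± 7"), and Week 168 is Day 1177 with the same window (Protocol 10.1.1.17).

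**Assumptions.** Constant hazard; 52-week incidence p between 1% and 30%; no unscheduled tests. The documents give none of these.

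**1. Where the curve steps.** (24+48)/2 = 36, (48+72)/2 = 60, (72+96)/2 = 84, (96+120)/2 = 108, (120+144)/2 = 132, (144+168)/2 = 156.

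**2. What each reading holds.** With F(t) = 1 − exp(−λt) and λ = −ln(1−p)/52, the reading at t equals F at the last assessment whose midpoint is at or before t. So 24 reads F(24), 52 reads F(48), 78 reads F(72) and 104 reads F(96). An onset at Week 50 is found at Week 72, dated Week 60, and missing from the 52-week value.

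**3. Size on schedule.** For a rare event, 48/52 = 72/78 = 96/104 = 0.923, or −7.7%. The 24-week value is unbiased. Percentage error by p:

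| p | 52 wk | 78 wk | 104 wk | 156 wk, step counted | 156 wk, step not counted |
|---|---|---|---|---|---|
| 1% | −7.7 | −7.6 | −7.6 | +7.6 | −7.6 |
| 5% | −7.5 | −7.4 | −7.3 | +7.1 | −7.2 |
| 10% | −7.3 | −7.1 | −7.0 | +6.5 | −6.6 |
| 20% | −6.9 | −6.6 | −6.2 | +5.3 | −5.5 |
| 30% | −6.5 | −5.9 | −5.4 | +4.1 | −4.5 |

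**4. The 156-week reading.** (1009 + 1177)/2 = Day 1093, which is 1,092 days after Day 1; 1092/7 = 156.0 weeks. Whether a PCSA first seen at Week 168 is counted therefore turns on small shifts in visit dates. If both visits deviate by a whole number of days, uniformly within ±7, there are 15 × 15 = 225 equally likely pairs. The midpoint is at or before 156 weeks in 120 of them (53%). If time is counted as date difference plus one day, it is 91 of 225 (40%).

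**5. Apparent trend, rare event.** Weeks 52–104 contain 96 − 48 = 48 weeks of onsets. Weeks 104–156 contain 48 weeks plus the counted share of the 24 weeks from 144 to 168.

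- About half counted: (48 + 12)/48 = 1.25
- 53% counted: (48 + 12.8)/48 = 1.27
- 40% counted: (48 + 9.7)/48 = 1.20
- All counted (every visit on schedule): 72/48 = 1.50
- None counted (every visit on schedule, plus-one-day count): 48/48 = 1.00

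**6. Simulation.** 400,000 patients per scenario, midpoint dating, censoring at the last assessment, p = 2% and 10%. Ratio is the cumulative hazard of weeks 104–156 over that of weeks 52–104; the true value is 1.

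| Scenario | Error at 52/78/104 wk, p = 2% | p = 10% | Error at 156 wk (2%, 10%) | Ratio (2%, 10%) |
|---|---|---|---|---|
| All to Week 168, ±7 days | −6.6/−6.5/−6.2 | −7.3/−6.9/−7.0 | +1.2, +0.5 | 1.24, 1.27 |
| End of treatment uniform, Weeks 120–168 | −7.8/−7.7/−7.8 | −7.2/−7.0/−7.2 | +4.0, +2.4 | 1.39, 1.36 |
| End of treatment uniform, Weeks 24–168 | −6.2/−4.6/−4.3 | −7.8/−7.5/−6.3 | +4.7, +2.0 | 1.27, 1.29 |

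Simulation error is 1–2%, judging by the 24-week reading, which should show no bias. Other assumed early-end patterns gave ratios between 1.23 and 1.40.

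**7. Against sampling error.** Simulated trials of 1,200 patients (5% per year, ±7 days, full follow-up) gave mean readings of 4.65%, 6.90%, 9.03% and 14.31% at 52, 78, 104 and 156 weeks. The true values are 5.00%, 7.41%, 9.75% and 14.26%.

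- At 52 weeks the shortfall is 0.35 points, against a standard error of √(0.05 × 0.95/1200) = 0.63 points.
- The increments are 9.03 − 4.65 = 4.38 and 14.31 − 9.03 = 5.28, a difference of 0.90 points. Its standard error is about √((0.0438 + 0.0528)/1200) = 0.90 points.
- The true increments, 4.75 and 4.51, differ by −0.24, so the full shift is 1.14 points, or 1.14/0.90 = 1.3 standard errors.

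**8. Check of the remedy.** Read at 24, 48, 72, 96 and 144 weeks, the same kind of curve gives 0.97–1.01 of the true incidence. The ratio of weeks 96–144 to weeks 48–96 is 0.95–1.02. Each of these weeks is at least six weeks from a midpoint (the nearest is (12+24)/2 = 18 for the liver panel), so ±7-day windows do not disturb the reading.

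**The case against.** The best counter-argument is that nothing is understated. No scheduled test falls in Weeks 48–52, 72–78 or 96–104, so the 52-, 78- and 104-week values equal the incidence observed by those weeks, and are low only against an onset time that nobody sees. This does not carry. Midpoint dating is a choice to estimate onset rather than detection. It also breaks the observed-incidence reading at 156 weeks, where about half of the PCSAs first seen at Week 168 would be counted twelve weeks before they are seen.

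Other points stand and limit the weight of the finding:

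- The analysis is exploratory, runs only after a signal, and is shown with the full curves, where the steps are visible.
- The crude PCSA incidence over the whole TEAE period is always reported and is unaffected.
- Both parent-treatment groups follow the same nominal schedule, so comparing them is largely unaffected.
- Unscheduled and repeat values count (SAP 2.4.5 and 2.5.5) and would shrink the error; their frequency is not given.
- The SAP plans no year-by-year rates, so a reader must subtract columns to see a rise.
- The landmarks match those for adverse events in SAP 2.4.5.1, which has some value.

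A reader might go further and infer that the table will show a false late rise, or that its values are 8% low throughout. The documents do not support either. The rise depends on visit timing at a single step, and 7.7% is the rare-event, on-schedule figure.

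**Conclusion.** The mismatch is real and follows from the plan's own schedule. Under a constant hazard and scheduled visits, the 52-, 78- and 104-week values are about 5–8% too low for 52-week incidences up to 30%; the 24-week value is sound. The 156-week value has no stable meaning. It can lie anywhere from about −8% to +8%, and is roughly unbiased when visits scatter within ±7 days.

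In that last case a constant risk looks about 25% higher in weeks 104–156 than in weeks 52–104. The rise vanishes only if every visit is exactly on schedule and time is counted as date difference plus one day.

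The artefact is about one standard error in one fully followed trial of 1,200 at 5% per year, and less relative to noise if fewer patients reach Week 156. It would not mislead dramatically on its own, but it is systematic and cheap to remove, so it should be corrected.

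**What to change.** In SAP 2.4.5.3 and 2.4.5.4, replace the reading times with scheduled assessment weeks: 24, 48, 72, 96, 120, 144, and 168 where enough patients remain. At those weeks the midpoint-dated curve gives the cumulative incidence up to that assessment.

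The cost is a change to two paragraphs and the column headings, with no new data or visits. The small downside is that PCSA and adverse-event Kaplan-Meier tables no longer share landmark weeks.

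If the shared landmarks are kept, use an interval-censored (Turnbull) estimate with a stated interpolation rule. At the least, footnote the last assessment that each value captures and do not take a reading at 156 weeks, where the curve steps.

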#### General common rules

All safety analyses will be performed on the safety population as defined in Section 2.3.2, unless otherwise specified, using the following common rules:

- The parent baseline value is defined as the last available value obtained up to the date and time of the first double-blind IMP injection in the parent study.
- The OLE baseline is defined as the last available value obtained up to the date and time of the first OLE IMP injection.
- PCSA values are defined as abnormal values considered medically important by the Sponsor according to predefined criteria/thresholds based on literature review and defined by the Sponsor for clinical laboratory tests, vital signs, and ECG (PCSA version dated January 2009 [Appendix A]). Considering that the threshold defined in the PCSA list for monocytes and basophils can be below the ULN, the following PCSA criterion will be used for the PCSA analysis:
  - PCSA criterion for monocytes: >0.7 Giga/L or > ULN (if ULN ≥0.7 Giga/L)
  - PCSA criterion for basophils: >0.1 Giga/L or > ULN (if ULN ≥0.1 Giga/L)
- PCSA criteria will determine which patients had at least 1 PCSA during the TEAE period, taking into account all evaluations performed during the TEAE period, including nonscheduled or repeated evaluations.
- The treatment-emergent PCSA denominator for a given parameter will be based on the number of patients assessed for that given parameter at least once during the TEAE period.
- All measurements, scheduled or unscheduled, fasting or not fasting, will be assigned to analysis windows defined in Section 2.5.4, Table 1 in order to provide an assessment for all planned time points.
- For quantitative safety parameters based on central laboratory/reading measurements, descriptive statistics will be used to summarize results and change from baseline values by

visit using analysis windows. Summaries will also include the last on-treatment value and the worst on-treatment value. The last on-treatment value is defined as the last value collected during the treatment period (see Section 2.1.4). The worst on-treatment value is defined as the nadir and /or the peak value during the treatment period according to the direction (minimum or maximum) of the abnormality as defined in the PCSA list.

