#### 2.4.5.4 Analyses of vital sign variables

The summary statistics (including number, mean, median, Q1, Q3, SD, minimum and maximum) of all vital signs variables in sitting position (raw values and changes from baseline will be calculated for each visit or study assessment (baseline, each post-baseline value of the treatment period, last on-treatment, worst on-treatment value and follow-up visit). In addition for some parameters of interest; mean changes from baseline with the corresponding SE could be plotted over time (at same time points excepted follow-up visit).

Vital signs without position filled in will only be used for the PCSA analysis described below.

The incidence of PCSAs at any time during the TEAE period will be summarized.

If any clinically significant signal is detected and needs further characterization, exploration of time to onset will be performed for selected PCSAs assessed during the TEAE period as described below to account for the differential exposure time in all patients.

The incidence rates of selected PCSA during TEAE period at 24, 52, 78, 104 and 156 weeks of exposure will be calculated with Kaplan-Meier methodology, using the midpoint of the time interval between the first assessment with PCSA and the previous assessment. Kaplan-Meier curves will be also provided. Only the first event (PCSA) will be counted. Patients without any event will be censored at the last assessment performed during the TEAE period.

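### The time-to-PCSA Kaplan-Meier rule does not limit the at-risk set to patients free of the abnormality at baseline, so a persisting Day 1 threshold abnormality counts as a new onset

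*SAP*

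**What the plan says.** The analysis is conditional. It opens with "If any clinically significant signal is detected and need further characterization", covers selected PCSAs only, and is meant to explore time to onset "to account for the differential exposure time in all patients". Incidence is read at 24, 52, 78, 104 and 156 weeks.

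The operating rule in SAP 2.4.5.3, repeated in 2.4.5.4, has three parts:

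- The event is dated "using the midpoint of the time interval between the first assessment with PCSA and the previous assessment".
- "Only the first event (PCSA) will be counted".
- "Patients without any event will be censored at the last assessment performed during the TEAE period".

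SAP 2.4.5, General common rules, sets the wider definitions. Safety analyses use the safety population unless stated otherwise. "PCSA criteria will determine which patients had at least 1 PCSA during the TEAE period", with no condition that the abnormality be new. The denominator for treatment-emergent PCSAs is "based on the number of patients assessed for that given parameter at least once during the TEAE period".

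The frequency tables in 2.4.5.3 do recognise patients who start out abnormal. They can be split into a normal/missing group and a group labelled "Abnormal according to PCSA criterion or criteria". The Kaplan-Meier paragraphs do not repeat that split.

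**The concern.** A time-to-onset curve should start from people in whom the event has not yet happened. Read with the general rules, the stated rule starts from everyone assessed. A patient already over a threshold on Day 1, and still over it at the next visit, has a first PCSA in the treatment-emergent period and so becomes an event.

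This matters for three reasons. Safety is the primary objective. The curve is produced only when a signal is suspected, which is when existing and new abnormalities most need separating. And SAP 2.4.5 presents safety results by parent treatment, so two groups with the same true onset rate would show different curves if their Day 1 prevalence differed. Patients from FH I, FH II and High FH enter at the parent end-of-treatment visit, so an abnormality that arose on parent alirocumab could raise Day 1 prevalence in that group and then appear as early onset in the extension.

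**Working it through.** **1. Is the restriction absent, or written elsewhere?**

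| Place in the SAP | At-risk restriction written? |
|---|---|
| 2.4.5.3 and 2.4.5.4, time-to-PCSA Kaplan-Meier | None |
| 2.4.5, General common rules | None: safety population by default; any PCSA in the period counts |
| 2.4.5.1, Kaplan-Meier for selected adverse events | Yes, for diabetes: only patients not diabetic at baseline |
| 2.4.6, time to first of two consecutive low LDL-C values | Yes: patients with fewer than two post-baseline results are left out |

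The SAP writes a restriction where it wants one. Nothing in the two PCSA sections overrides the default population.

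**2. Can a patient meet a PCSA on Day 1?** Yes, for threshold criteria. SAP 2.4.5 gives monocytes above 0.7 Giga/L and basophils above 0.1 Giga/L, and 2.5.3 gives eosinophils above 0.5 Giga/L, each with an alternative tied to the upper limit of normal. Criteria that require a change from baseline cannot in general be met by the baseline value itself. SAP 2.5.3 falls back on the threshold or normal-range part of a two-condition criterion when the change part is missing. Appendix A is not in the supplied text, so the share of threshold-type PCSAs cannot be counted.

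**3. What date does such a patient get?** Hematology and chemistry are taken at Weeks 0, 8 and 24 and every 24 weeks after that (SAP 2.1.4.3). The midpoint is (0 + 8)/2 = Week 4. The liver panel is also taken at Week 4, as are heart rate and blood pressure (protocol 1.2), which gives (0 + 4)/2 = Week 2.

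**4. Size at Week 24.** The plan states no figure to reproduce. Let p be PCSA prevalence on Day 1, s the share still abnormal at the next assessment, and I the true 24-week incidence of new PCSAs. All three are assumptions. Then

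rule as written = p·s + (1 − p·s)·I

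The restricted analysis gives I. Extra cases among 1,200 patients = 1,200·p·s·(1 − I). With I = 2%:

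| p | s | Calculation | Reads | Ratio to 2% | Extra cases in 1,200 |
|---|---|---|---|---|---|
| 0 | any | 0 + 0.02 | 2.00% | 1.00 | 0 |
| 1% | 50% | 0.005 + 0.995 × 0.02 | 2.49% | 1.25 | about 6 |
| 1% | 80% | 0.008 + 0.992 × 0.02 | 2.78% | 1.39 | about 9 |
| 5% | 80% | 0.040 + 0.960 × 0.02 | 5.92% | 2.96 | about 47 |
| 10% | 80% | 0.080 + 0.920 × 0.02 | 9.84% | 4.92 | about 94 |

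Two parent-treatment groups with the same 2% true incidence and 80% persistence, but Day 1 prevalence of 1% and 5%, would read 2.78% and 5.92%.

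**5. Later landmarks, and the part played by the midpoint.** Kaplan-Meier curves were simulated for 200,000 patients on the SAP laboratory schedule, assuming 2% per year new onset and 8% per year dropout:

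| Analysis | Wk 24 | Wk 52 | Wk 78 | Wk 104 | Wk 156 |
|---|---|---|---|---|---|
| Restricted to PCSA-free at baseline, midpoint | 0.94% | 1.85% | 2.75% | 3.64% | 6.31% |
| As written, p = 5%, s = 80%, midpoint | 4.91% | 5.78% | 6.64% | 7.49% | 10.06% |
| Same patients, event dated at the visit | 4.91% | 5.78% | 6.64% | 7.49% | 9.20% |

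The excess is 3.97 percentage points at Week 24 (4.91 − 0.94) and still 3.75 at Week 156 (10.06 − 6.31). Changing the dating method leaves the first four landmarks unchanged. At Week 156 it matters only because the midpoint of Weeks 144 and 168 falls exactly on the landmark. The risk set therefore produces the excess.

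**The case against.** The strongest reply is that the SAP never says it keeps these patients. The phrase about all patients describes differing exposure; it does not define a risk set. The analysis is exploratory and left to be specified if a signal appears. That is fair as far as intent goes: a reader might infer a deliberate choice to count prevalent cases, and the text does not show one. But event, date and censoring are all specified, the default population is the safety population, and someone programming from the text would include these patients.

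Second, SAP 2.4.5 already requires PCSAs by baseline status, against both baselines, so a reader would have the context. This stands in part. Those tables are crude proportions, the laboratory wording makes the split optional, 2.4.5.4 lists no baseline categories of its own, and none of this corrects the curve.

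Third, any bias overstates harm, which is the cautious direction. That is true of a single curve. It does not hold for a comparison of parent-treatment groups, where the distortion follows whichever group has more persisting Day 1 abnormalities.

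Fourth, excluding on the extension baseline alone could remove abnormalities that arose on parent-study alirocumab. This objection stands in full and shapes the fix.

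Three stronger readings should be resisted:

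- *The midpoint rule inflates incidence.* Step 5 shows that it does not at Weeks 24 to 104.
- *The result is wrong whenever the analysis is run.* With no persisting baseline prevalence there is no inflation, and change-from-baseline criteria are generally outside the problem.
- *The 24-week figure measures prevalence more than onset.* This depends on the assumptions. At 2% prevalence and 80% persistence, prevalent cases supply 1.6 of about 3.6 points, less than half.

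**Conclusion.** The point holds as a defect in the risk set. Followed as written, the rule counts a persisting Day 1 threshold abnormality as a first onset at about Week 2 or Week 4, and the excess carries through to every landmark.

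The size cannot be taken from the documents. On assumed values around a true 24-week incidence of 2%, it runs from none (zero prevalence), through a quarter too high (1% prevalence, 50% persistence), to nearly five times too high (10% prevalence, 80% persistence). The result rests on threshold-type PCSAs with some persisting baseline prevalence. The SAP's own abnormal-at-baseline category shows that such patients are expected, but not how many.

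Because the analysis is conditional, descriptive and tied to no test, this should be corrected but does not threaten the main safety tables.

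**What to change.** In SAP 2.4.5.3 and 2.4.5.4, add text to this effect: each time-to-PCSA Kaplan-Meier analysis includes only patients without that PCSA at baseline; it is run with the OLE baseline and repeated with the parent baseline; patients with the PCSA at baseline are reported separately.

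Both baselines are already used under SAP 2.4.5. The parent-baseline run keeps visible any abnormality that arose on parent-study alirocumab. Its early step will include abnormalities already present on Day 1 of the extension, so it should be labelled as onset since the parent baseline and its early dates not read as extension onset.

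Also say how a missing baseline is handled. SAP 2.5.3 groups missing with normal, so a few possible prevalent cases would remain; giving their number is enough.

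The cost is one or two sentences per section using a category already derived, a slightly smaller risk set for common PCSAs, and one extra run of a conditional, exploratory analysis.
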